Also, with the aim of avoiding activation-inhalation incoordination, ICPs have been developed that are triggered automatically with the patient's inspiration, such as the Autohaler® and Easybreath®, which have been shown to improve the pulmonary deposition of the drug in patients with coordination difficulties. They also require a lower inspiratory flow than conventional ICPs, around 18-30 L/min, which makes them more suitable for patients with physical limitations, children, and the elderly.

Primary Objectives

- Compare the efficacy, as measured by changes in forced expiratory volume in the first second (FEV1) in miliLiters of inhaled Salbutamol with the Dosivent® chamber versus the widely used Aerochamber Plus® Flow-Vu® in patients with a positive Bronchodilator testing.
- Compare the efficacy, as measured by changes in forced expiratory volume in the first second (FEV1) in percentage of inhaled salbutamol with the Dosivent® chamber versus the widely used Aerochamber Plus® Flow-Vu® in patients with a positive Bronchodilator testing.

Secondary Objectives

- Compare the efficacy, as measured by changes in forced vital capacity (FVC) in miliLiters, of inhaled Salbutamol with the Dosivent® chamber versus the widely used Aerochamber Plus® Flow-Vu® in patients with a positive Bronchodilator testing.
- Compare the efficacy, as measured by changes in forced vital capacity (FVC) in percentage, of inhaled Salbutamol with the Dosivent® chamber versus the widely used Aerochamber Plus® Flow-Vu® in patients with a positive Bronchodilator testing.

Number of Patients

Approximately 50 patients with a diagnosis of Bronchial Hyperreactivity will be included in the study.

Methodology

The investigators are conducting a non-randomized, open-label, crossover-controlled clinical trial in 50 patients with a previous positive bronchodilation testing. The protocol was approved

by the local clinical ethics committee (code 03/2022). All participants provided written informed consent before any study procedure. During the study, the principles of the Declaration of Helsinki and the current standards of Good Clinical Practice were followed.

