Participants over 18 years of age are included who attended our center for a bronchodilator test, gave a positive result in this test, and provided written informed consent for participation in this study. Patients are excluded if grade A quality spirometry was not obtained according to the classification in current regulations and, in the opinion of the investigator, performing a bronchodilator test could pose a risk to the patient or interrupting the usual bronchodilator treatment could worsen the underlying respiratory pathology.

Inclusion Criteria:

- Patients over 18 years of age
- Attending our center for a bronchodilator test
- Positive bronchodilator result with increase of Forced Expiratory Volume in first second greater than 200mL and 12%
- Provided written informed consent for participation in this study

Exclusion Criteria:

- Grade A quality spirometry was not obtained according to the classification in current regulation
- Performing a bronchodilator test, in the opinion of the investigator, could pose a risk
 to the patient or interrupting the usual bronchodilator treatment could worsen the
 underlying respiratory pathology.

Determination of sample size

To achieve a statistical power of 80% in order to detect differences in the test of the null hypothesis H_0 : μ_1 - μ_2 = 0 for two related samples, with a significance level of 0.05, it will be necessary to include 45 patients in the study. Taking into account that the expected percentage of dropouts is 5%, it would be necessary to recruit 50 subjects for the study.

Statistical Methods

The primary analysis will be performed by intention to treat according to the following table:

Population	Description All patients registered in the study database; includes both screened participants and participants who are not selected but sign the informed consent (IC) form	
All patients included		
By modified intention to treat	All randomized patients receiving at least one dose of study treatment. Participants will be analyzed according to the treatment to which they were randomly assigned. The intention-to-	

	treat population will be used for all efficacy summaries	
Protocol population (PP)	The PP is comprised of the intention-to- treat population, excluding any participant with a major deviation from the protocol. The PP will be used to present sensitivity analyzes for the key endpoints.	

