Safety population	All randomized participants receiving at least one dose of study treatment. Participants will be analyzed according to the treatment they actually received. The safety population will be used for all safety summaries	

Parameter differences will be described as mean and standard deviation if the normality of the mean differences can be verified; otherwise, they will be described as median and interquartile range. The proportions will be described with their standard error.

Study variables will be analyzed using linear mixed models representing repeated measures in which patient will be the random effect and treatment and study phase will be the fixed effects.

Schedule of Activities (SoA)

Visit 1		Visit 2	
Informed Consent	X		
Inclusion and Exclusion	X		
Criteria			
Medical History	X		
Inhaled Therapy Medication	X		
Randomization	X		
Spirometry with	X	X	
Bronchodilator Testing			
Clinical Registry	X	X	

Procedures

Informed consent must be signed prior to any screening assessment.

Patients with Bronchial Hyperreactivity, defined by a positive Bronchodilator Test, will be offered the study through a patient information sheet and informed consent from the patient. A positive bronchodilator test is defined as patients with an improvement in forced expiratory volume in the first second (FEV1) of 200mL and an increase of 12% after 15-30 minutes of application of 4 puffs of Salbutamol in a pressurized cartridge with the Aerochamber Plus Flow air chamber. Vu according to usual clinical practice. Once the patient has signed the informed consent, they will be summoned to perform said test again on another day, having already passed the 6-hour Salbutamol washout period. Subsequently, a comparison will be made with a Delta limit of non-inferiority of 3%.

Bibliography

- Byron P. Drug Delivery Devices. Issues in Drug Development. Proc Am Thorac Soc Vol 1.
 Pp. 321-328, 2004.

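### The plan contradicts itself on randomisation and never says which tests are compared, so the primary contrast and its analysis population are not determined

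*Combined protocol and SAP*

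**What the plan says.** All places are in the combined protocol and SAP.

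- **Methodology** describes a "non-randomized, open-label, crossover-controlled clinical trial in 50 patients with a previous positive bronchodilation testing". It adds: "All participants provided written informed consent before any study procedure".
- **Statistical Methods** defines the modified intention-to-treat population as "All randomized patients receiving at least one dose of study treatment", and continues: "Participants will be analyzed according to the treatment to which they were randomly assigned". This population serves all efficacy summaries. The per-protocol population is drawn from it. The safety population is "All randomized participants receiving at least one dose of study treatment". The planned analysis is a linear mixed model with a random patient effect and fixed effects for treatment and study phase; phase is not defined.
- **Schedule of Activities** marks Randomization at Visit 1 and bronchodilator spirometry at Visits 1 and 2, with no chamber or order.
- **Inclusion Criteria** require "Positive bronchodilator result with increase of Forced Expiratory Volume in first second greater than 200mL and 12" per cent.
- **Procedures** says the qualifying test uses the Aerochamber under usual practice. After consent, "they will be summoned to perform said test again on another day, having already passed the 6-hour Salbutamol washout period". No chamber is named for that repeat. A comparison with a non-inferiority limit of 3% follows.
- **Primary Objectives** compare the two chambers "as measured by changes in forced expiratory volume in the first second (FEV1) in miliLiters of inhaled Salbutamol", and again in per cent. Dosivent is named in the title and the objectives, but at no test.

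**The concern.** A comparison of two chambers within patients needs three facts: which chamber is used at which test, how the order is set, and which tests enter the analysis. The plan contradicts itself on the second and is silent on the first and third. An analyst could not build the efficacy population or the treatment variable from this text.

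The answers decide whether the result can be interpreted. A test that admitted the patient because its response was high is not a fair comparator for one that faced no such filter. Separately, if one chamber always comes first, anything that changes between visits is counted as a device effect.

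**Working it through.** **1. Populations.** Four are defined: all included, modified intention-to-treat, per-protocol and safety. The second and fourth require randomisation, and the third is a subset of the second. In a trial that is literally non-randomised, 3 of 4 are empty, including the one used for efficacy.

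**2. Readings that the text allows.**

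| Reading | Support | Selection bias | Device and visit aliased |
|---|---|---|---|
| A. Qualifying Aerochamber test is the comparator; the single repeat uses Dosivent | Sequence in Procedures; non-randomised label | Yes | Yes |
| B. Separate qualifying test, then two study tests in random order | Randomization row; randomised populations; phase term; consent before screening | No | No |
| C. The repeat is literally the Aerochamber test again | Wording of the repeat in Procedures | Undefined: Dosivent has no place | Undefined |
| D. Separate qualifying test, then two study tests in fixed order | Non-randomised crossover label with a previous positive test; two tests in the Schedule | No | Yes |

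**3. Aliasing.** Fixed-effects matrix with columns for intercept, treatment and visit, two tests per patient. Fixed order: the treatment and visit columns coincide, rank 2 of 3. Both orders present: rank 3 of 3. This assumes that study phase means visit.

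**4. Selection effect, when the qualifying test is reused.** The plan has no figure to reproduce here. Its sample size (45 evaluable) comes without an effect size or SD, so no variability can be taken from it.

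Assumed: percentage FEV1 change is normal among tested patients, with mean μ of 6 to 12, SD σ of 6 to 8 and test-retest correlation ρ; the chambers are identical; there is no period effect; only the 12% criterion is applied. Then

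E[X₁ − X₂ | X₁ > 12] = (1 − ρ)·S, where S = σ·φ(z)/(1 − Φ(z)) and z = (12 − μ)/σ.

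- Smallest S: μ = 12, σ = 6, z = 0, so S = 6 × 0.399/0.5 = 4.79.
- Largest S: μ = 6, σ = 8, z = 0.75, so S = 8 × 0.301/0.227 = 10.63 (unrounded inputs).

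| ρ | Spurious Dosivent deficit, points |
|---|---|
| 0.9 | 0.5–1.1 |
| 0.8 | 1.0–2.1 |
| 0.7 | 1.4–3.2 |
| 0.6 | 1.9–4.3 |
| 0.5 | 2.4–5.3 |

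Reading the margin as 3 percentage points, the deficit equals it at ρ = 1 − 3/S, which is 0.37 to 0.72.

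**5. Sensitivity.** Simulating both entry criteria with a pre-dose FEV1 mean of 1600 mL (SD 600, μ = 6, σ = 8) moves the upper break-even to 0.735 and the deficit at ρ = 0.5 to about 5.65 points. A separate simulation on the mL scale assumed pre-dose FEV1 of 2000 mL (SD 500), mean response 150–350 mL, between-patient SD 100–150 mL and within-patient SD 50–150 mL. It gave 0.35 to 7.8 points (7 to 141 mL), against Dosivent in all 24 scenarios.

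In its middle case (mean 250, between-patient SD 150, within-patient SD 100) the deficit is 42 mL or 2.3 points. With 45 pairs and a two-sided 95% interval, identical chambers are then shown non-inferior in 9% of trials, against 67% with a fresh Aerochamber test. Dosivent is falsely found worse in 48%, against 2.5%.

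**The case against.** The strongest reply is that the intended design is probably B. Consent before any screening, the Randomization row, the randomised populations and the phase term all fit it, and under B there is neither selection bias nor aliasing. That stands as an argument against asserting bias, but it does not settle the design: the non-randomised label and the single repeat in Procedures point elsewhere.

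Four stronger readings are tempting, and the documents do not support them.

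- *The comparison is biased against Dosivent.* This holds only if the qualifying test is reused, which no section says. A non-randomised trial with a separate qualifying test (D) has no such bias, only aliasing.
- *The error can only hurt Dosivent.* Only the selection component has a known direction. Under reading A the order is also fixed, so a period or learning effect could add to the deficit, offset it, or mask a poorer chamber.
- *Procedures and the Schedule flatly disagree on one test versus two.* If the Visit 1 test is the qualifying test, both give two in all. What then remains open is how consent can precede a test whose positive result leads to the invitation.
- *Good repeatability makes the bias harmless.* No universal threshold exists. The break-even correlation moves with the assumptions, as does the simulated power: with between-patient SD 10, within-patient SD 5 and mean 12 points, reuse gives non-inferiority in about 20% of trials; with between-patient SD 6 it is about 5%.

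**Conclusion.** The point holds as a contradiction and a missing specification, and on that basis it must be fixed. From the text alone, three of four analysis populations conflict with the stated design, and neither the test at which Dosivent is used nor the source of the Aerochamber value is given.

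The two consequences are conditional and distinct. Reuse of the qualifying test brings a selection deficit against Dosivent. Fixed order, with or without reuse, makes device and visit inseparable in the planned model. The size of the deficit rests wholly on assumed means, SDs and correlations and on reading the 3% margin as percentage points. It can be small or larger than the margin, and the need for a fix does not depend on it.

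**What to change.** 1. Reconcile Methodology, Statistical Methods, the Schedule of Activities and Procedures on whether chamber order is randomised, and name the chamber used at each test.
2. State that the test used for eligibility does not enter the efficacy comparison, and take that comparison from two post-eligibility tests, one per chamber.
3. If order is randomised as the Schedule shows, correct the non-randomised label and define study phase as period.
4. If order is in fact fixed, redefine the modified intention-to-treat, per-protocol and safety populations without randomisation, drop the phase term, and state that the device effect is confounded with order.
5. If the qualifying test is in fact the Aerochamber value, so that step 2 cannot be met, state in addition that the comparison carries selection bias against Dosivent.

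**Cost.** Wording only where a separate earlier test qualifies patients and order is randomised. The statements of limits in steps 4 and 5 are also wording only. An extra test visit per patient, or randomisation newly introduced, would not be cheap and is not required here.
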